8.2 REFERENCE SAFETY INFORMATION: POTENTIAL ADVERSE REACTIONS

Over 500 patients have been treated using Xilonix in patients with advanced solid tumors, advanced hematologic malignancies, metastatic colorectal cancer, peripheral vascular disease, type II diabetes, acne vulgaris, plaque psoriasis, and pyoderma gangrenosum. Over 1200 doses of Xilonix were administered at 7.5 mg/kg to refractory, metastatic CRC patients with cancer associated symptoms at baseline (ECOG performance status 1 and 2). In this trial (PT026), which is the largest controlled trial completed with Xilonix to date (N=309), patients were dosed at 7.5 mg/kg for metastatic colorectal cancer. The most common AEs reported (>10%) were abdominal pain, peripheral edema, fatigue, anemia, constipation, decrease in weight, asthenia, decreased appetite, and nausea. The majority of these events were grade 1 or 2, and appeared to be related to the underlying CRC. The prevalence of these events was similar in the Xilonix and placebo groups. Two infusion reactions were reported in this trial, and they were not serious or severe (grade I or II).

The RSI has been updated based upon data from a randomized, double-blind, placebo controlled trial in metastatic colorectal cancer (2014-PT026), which was recently completed. In this trial, there was no difference in the incidence of thrombocytopenia, proteinuria, nausea, or diarrhea, between the two groups; therefore these terms were removed from the list of expected adverse reactions (ARs). There were two infusion reactions that occurred in the PT026 trial, as well as one infusion reaction reported as an SAE in the PT023 trial.

The mechanism behind infusion reactions is not clear in all cases. It may involve a reaction against the antibody products themselves, or, against some minor residual component from the manufacturing process (i.e. host cell proteins). To date, after administration to over 500 patients, and over 3000 doses, the risk of infusion reaction remains extremely low.

For the purposes of expedited safety reporting in clinical trials, the following should be considered expected events:

- **Infusion Related Reactions**

Refer to Section 4.6 of the Investigator's Brochure for clinical trial summaries of Xilonix, and Section 5 for a Summary of Data and Guidance for the Investigator.

8.3 Overall Risk and Benefit Assessment

Chemotherapy and radiotherapy in the context of advanced metastatic or unresectable colorectal cancer is largely palliative—meaning that complete eradication of the tumor is not expected. The primary goal in this setting is reducing symptomatic effects of the tumor for as long as possible. Due to toxicity, however, these treatment modalities are poorly suited for this objective. Even with the most recent agents (such as multi-kinase inhibitors) treatment related morbidity often results in discontinuation of therapies—ultimately leading to uncontrolled progression and death. New agents that exhibit anti-neoplastic activity and provide improvement in tumor related symptoms are vitally needed to treat this and other advanced cancer populations.

Specific antagonism of IL-1 α through Xilonix™ therapy is viewed as a unique, broad acting tumor suppression strategy that encompasses significant activity to ameliorate symptoms associated with the disease, as well as improve overall survival. IL-1 α is unique in its involvement in so many processes related to tumor progression and collateral symptomatic effects of malignancy. The excellent safety and tolerability profile of the agent make it an ideal treatment option in advanced stage disease, particularly where the use of cytotoxic or other therapies with considerable toxicity are not supported by the risk benefit profile.

Blocking IL-1 α appears to normalize the metabolic energy balance with the net accumulation of lean body mass (LBM). An average LBM increase of 1.9 \pm 2kg was seen in 70% of patients treated ($p < 0.001$) compared to their baseline values. These same patients had improvements in pain, anorexia, and fatigue as measured by the EORTC-QLQ-C30. Traditional, radiographic evidence of anti-tumor activity was also noted, with 21% of patients having stable disease for 3 months or greater, including a partial response in a patient with metastatic colorectal cancer. Additionally, colorectal cancer patients with improvements in LBM had a trend towards a clinically significant overall survival benefit.

For this agent, this reversal of tumor related symptoms, is viewed as the direct result of an anti-neoplastic mechanism of action and is potentially a more powerful surrogate for clinical benefit than traditional radiographic based assessments. In the tumor microenvironment IL-1 α driven sterile inflammation results in neoangiogenesis and tissue matrix remodelling both of which are critical for tumor growth. Within the vascular space, membrane associated IL-1 α on PBMCs and platelets activate vascular endothelium, which in turn leads to upregulation of adhesion molecules and further infiltration of the microenvironment by pro-tumor inflammatory cells. Activation of the vascular endothelium also provides a mechanism by which tumor cells (in the form of tumor-platelet microemboli) can escape into new areas of metastasis.

The importance of IL-1 α to tumor growth and invasiveness has been illustrated in numerous pre-clinical models, as well as from studies examining biopsies of multiple tumor types. However, the most compelling evidence to date is that illustrated in our pilot oncology trial, 2009-PT004.

Radiographic evidence of tumor regression has been observed in some cases, and multiple patients have experienced prolonged stable disease. Adverse events observed in these oncology patients have been mild, with 97% being grade 2 or lower in severity. These events have also shown no obvious relation to study drug administration.

Xilonix is a non-toxic, anti-neoplastic agent that has shown preliminary evidence of improving both metabolic and functional symptoms in patients who have exhausted all lines of anti-tumor therapy. The demonstration of LBM increases in advanced stage patients with a non-anabolic agent could represent a significant milestone in the management of metastatic cancer, as well as a novel surrogate for anti-neoplastic activity in refractory patients. Based upon these observations, the risk benefit analysis of Xilonix appears to be favourable and this therapy should be explored further advanced cancer patients.

9. ADVERSE EVENTS

9.1 DEFINITION OF ADVERSE EVENT (AE)

An adverse event is defined as any new or worsening untoward medical occurrence in a subject participating in a clinical study that does not necessarily have a causal relationship with the pharmaceutical or biological agent under study. An AE can therefore be any of the following:

- Any unfavorable and unintended sign (including laboratory findings), symptom, or disease temporally associated with the use of MABp1, whether or not it is apparently related to MABp1
- A concurrent illness
- An exacerbation, or an unexpected increase in frequency or intensity of a preexisting condition, including intermittent or episodic conditions.
- A significant or unexpected worsening of the condition/indication under investigation. However, anticipated day-to-day fluctuations or non-serious, expected progression of the disease under investigation (based upon the Investigator's clinical judgment) are not to be considered AEs
- A suspected interaction between the investigational drug and concomitant medications
- Any clinically significant laboratory abnormality (including radiological interpretations, histopathological findings, etc.)

9.2 DEFINITION OF SERIOUS ADVERSE EVENT (SAE)

A serious adverse event is defined as any untoward medical occurrence that meets any of the following criteria:

- Results in death
- Life-threatening
- Requires or prolongs inpatient hospitalization
- Results in a persistent or significant disability or incapacity
- Congenital anomaly/birth defect or
- An important medical event that, while it may not result in death or be immediately life-threatening or require/prolong hospitalization, may jeopardize the subject and/or may require medical or surgical intervention to prevent one of the outcomes listed above. Examples of such events are intensive treatment in an emergency room or at home for allergic bronchospasm; blood dyscrasias or convulsions that do not result in hospitalization; or the development of drug dependency or drug abuse.

Note that seriousness and severity should not be confused. A subject could experience a severe headache that would not qualify as an SAE, while another might experience a mild stroke that, while not severe, would be considered serious.

9.3 RECORDING OF ADVERSE EVENTS

All untoward events occurring between Cycle 1 Day 1 and 30 days following the last administration of the investigational drug must be recorded on the eCRF, regardless of whether they are considered related to study drug or not.

All AEs should be recorded in a standard medical terminology as concisely as possible. The AE recorded should not be a procedure or a clinical/laboratory measurement, but should reflect the event leading to the procedure or the cause of the clinical/laboratory abnormality, if known.

Whenever possible, AEs should be evaluated and recorded as a diagnosis, rather than individual signs and symptoms. However if a definitive diagnosis is not possible, the individual signs and symptoms should be recorded. Any AE that worsens in intensity, or becomes serious, should be recorded as a new event.

9.4 EVALUATING ADVERSE EVENTS

All AEs will be graded according to the CTCAE version 4.0.

9.5 ASSESSMENT OF CAUSALITY

Investigators are required to assess the relationship, if any, of each AE or SAE to the investigational drug using clinical judgment to determine the degree of certainty with which an AE can be attributed to the investigational drug. Alternative causes, such as natural history of the underlying disease, other risk factors, and the temporal relationship of the event to the administration of the study medication must be considered.

Relationship to study drug is summarized as follows:

- **Not Related:** There is another obvious cause of the AE
- **Unlikely to be related:** There is another more likely cause of the AE
- **Possibly related:** The AE could have been due to the investigational drug
- **Probably related:** The AE is probably attributable to the investigational drug
- **Definitely related:** The AE is most likely attributable to the investigational drug

9.6 REPORTING REQUIREMENTS

All serious adverse events (SAEs) should be reported to the Sponsor within 24 hours of knowledge of the event. These immediate reports should be followed promptly by detailed, written reports. The immediate and follow-up reports should identify subjects by unique code numbers assigned to the trial subjects rather than by the subjects' names, personal identification numbers, and/or addresses. The Investigator should also submit SAEs to the IRB/EC according to their IRB/EC guidelines [ICH-GCP E6]. Drug-related Serious Adverse Events will be reported to the FDA by XBiotech's Medical Safety Officer according .32.

9.7 SAFETY LEAD IN PLAN

In order to more accurately characterize the adverse event profile at the 7.5 mg/kg dose level, the Sponsor will conduct a blinded review of adverse event data for the first 10+10 patients enrolled on this protocol at that dose level. Review of the data will occur after completion of 2 cycles (28 days) of therapy for the first 10 patients, and then again after the second 10 patients. As there is a 2:1 randomization, approximately 6 of the first 10 and 13 of the first 20 patients will have received Xilonix™. A report of the adverse event data at each of these two time points will be submitted to the FDA within 10 days of the last patient's completion of 2 cycles.

The Sponsor will voluntarily suspend enrollment on the study, immediately and at any time upon review of safety data during the lead in period, if $\geq 33\%$ (≥ 6) of patients have experienced a dose limiting toxicity (DLT). In this event, enrollment will be suspended pending further IDMC review and pending further guidance from the FDA. Under these circumstances, the IDMC will be asked to review un-blinded data and make a recommendation regarding the safety of the dose level in this population.

A DLT will be defined as a clinically significant adverse event or abnormal laboratory value assessed as unrelated to disease progression, intercurrent illness, or concomitant medications occurring during the first two cycles (i.e. 28 days) of therapy, with relationship to study drug determined as possible, probable, or definite and meeting the criteria as Grade 3 or Greater Hematological or Non-Hematological Toxicity as assessed by the CTCAE V4.0.

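### The safety lead-in trigger gives 33% and 6 patients as one rule, but they conflict at both scheduled reviews (10 and 20 patients)

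*Protocol*

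**What the plan says.** Protocol section 9.7 (Safety Lead In Plan) covers early patients given 7.5 mg/kg. Its plan is blinded and runs in two steps: "the Sponsor will conduct a blinded review of adverse event data for the first 10+10 patients enrolled on this protocol at that dose level". The first scheduled look is set by this sentence: "Review of the data will occur after completion of 2 cycles (28 days) of therapy for the first 10 patients". A further look follows once another 10 have been treated, so the cumulative sizes are 10 and 20.

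The sponsor is to suspend enrolment "if $\geq 33\%$ (≥ 6) of patients have experienced a dose limiting toxicity (DLT"). The trigger is not confined to the two looks; it operates "immediately and at any time upon review of safety data during the lead in period". Suspension then leads to unblinded IDMC review and a wait for FDA guidance.

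The section prints one other pair of denominators, the expected numbers on active drug: "approximately 6 of the first 10 and 13 of the first 20 patients will have received Xilonix™". A DLT must be grade 3 or greater, at least possibly related to study drug, and "occurring during the first two cycles (i.e. 28 days) of therapy".

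Neither the SAP nor any other part of the protocol restates the trigger or says whether the percentage or the count governs.

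**The concern.** A count in brackets after a percentage reads as the same threshold in patients. Here that cannot be so, because one fixed count cannot equal one fixed percentage at two different review sizes, and 6 matches 33% at neither of them.

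The conflict also changes direction. At 10 patients the count is the laxer half; at 20 it is the stricter half. A reader therefore cannot tell from the text which half was meant to control, or whether one or both must be met.

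This is the only numerical suspension threshold for the lead-in. Two people applying the same sentence to the same blinded data could reach opposite decisions on whether enrolment stops.

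**Working it through.** **Inputs (all from Protocol section 9.7).** Percentage half: at least 33%. Count half: at least 6. Scheduled review sizes: 10 and 20, both arms pooled because the review is blinded. Expected Xilonix patients: about 6 and 13.

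**Step 1. Try to reproduce the bracketed 6.** The smallest whole number of patients r with r/n ≥ 0.33 is 0.33 × n rounded up.

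| Denominator n | 0.33 × n | Smallest count meeting 33% | 6 as a share of n |
|---|---|---|---|
| 10 (first review) | 3.30 | 4 (3/10 = 30%, 4/10 = 40%) | 60% |
| 20 (second review) | 6.60 | 7 (6/20 = 30%, 7/20 = 35%) | 30% |
| 6 (expected Xilonix, first 10) | 1.98 | 2 | 100% |
| 13 (expected Xilonix, first 20) | 4.29 | 5 | 46% |

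No denominator printed in the section gives 6. Using exactly one third instead of 0.33 changes none of these counts (10/3 = 3.33, 20/3 = 6.67). The Xilonix-only denominators could not be applied in a blinded review anyway.

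**Step 2. Find where the halves do agree.** For every n from 6 to 20, the rounded-up count equals 6 only at n = 16, 17 and 18 (6/18 = 33.3%). Neither scheduled review has that size.

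**Step 3. Find the outcomes where the decision differs.**
- At 10 patients, 4 or 5 DLTs: the percentage suspends, the count does not.
- At 20 patients, exactly 6 DLTs: the count suspends, the percentage does not.
- At every other total at these two reviews, the halves give the same decision.

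**Step 4. How often that happens.** The documents give no pooled DLT rate, so the rates below are assumptions. With X following a binomial(n, p) distribution, the readings disagree with probability P(X = 4 or 5) at n = 10 and P(X = 6) at n = 20. All figures are exact binomial, in percent, with differences taken before rounding.

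| Assumed rate p | n = 10: P(X ≥ 4) | n = 10: P(X ≥ 6) | n = 10: disagree | n = 20: P(X ≥ 6) | n = 20: P(X ≥ 7) | n = 20: disagree |
|---|---|---|---|---|---|---|
| 10% | 1.3 | 0.01 | 1.3 | 1.1 | 0.2 | 0.9 |
| 20% | 12.1 | 0.6 | 11.5 | 19.6 | 8.7 | 10.9 |
| 30% | 35.0 | 4.7 | 30.3 | 58.4 | 39.2 | 19.2 |
| 40% | 61.8 | 16.6 | 45.1 | 87.4 | 75.0 | 12.4 |
| 50% | 82.8 | 37.7 | 45.1 | 97.9 | 94.2 | 3.7 |

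At lower assumed rates the disagreement is smaller: 0.10% (n = 10) and 0.03% (n = 20) at a rate of 5%, and 4.9% and 4.5% at 15%.

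**The case against.** The arithmetic is not in dispute; the case on the other side is about how much it matters.

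- **The 6 may be 33% of the full 20, rounded down.** That is plausible but inferred. 33% of 20 is 6.6, and 6/20 = 30% fails the stated minimum of 33%. It would also leave the 10-patient review unsettled, where 6 is 60%.
- **The trigger applies at any time, and the halves agree at 16 to 18 patients.** True, but this adds further sizes where they do not agree. The percentage half means 3 or more at 7 to 9 patients and 5 or more at 13 to 15, while the count stays at 6.
- **The band of disagreement is narrow and DLTs may be rare.** This stands as a limit on size. The DLT definition is restrictive and about one third of patients receive placebo. Protocol section 8 describes mostly low-grade events, with prevalence similar to placebo in the completed trial at 7.5 mg/kg. At pooled rates of 10% or less the readings would seldom differ. A suspension rule exists, however, for the case where the rate is higher than expected.
- **Other safeguards exist.** Adverse event reports go to the FDA at both time points whether or not the trigger fires, SAP section 4 has continuous monitoring for early toxicity until the first interim analysis, and Protocol section 5.1 has patient-level rules. These reduce the consequence, but none of them says which half of the trigger governs.
- **The lead-in may already be over.** The documents do not say so. If it is, the record should still show which threshold was applied.

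**Conclusion.** The concern holds. As written, the trigger contradicts itself at both scheduled reviews, and nothing in either document resolves it. The decision depends on the reading at 4 or 5 DLTs among 10 patients and at exactly 6 among 20.

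The practical size rests on the assumed pooled DLT rate: about 1% at each review if the rate is 10%, about 11% at each if it is 20%, and 30% and 19% if it is 30%. These figures also assume that patients are independent and that all patients reviewed count in the denominator. Section 9.7 does not say whether the denominator is patients enrolled, dosed, or through 28 days.

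The effect is confined to the lead-in suspension decision. The overall survival sample size, alpha and power do not change. Because this is a safety decision threshold and the correction is small, it should be corrected.

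**What to change.** Reconcile the percentage, the count and the two review sizes in Protocol section 9.7. State one count for the 10-patient review and one for the 20-patient review, each with the percentage it represents. In the same place, define the denominator and say how the trigger is applied between the two reviews, since the text allows action at any time. Which values to use is a clinical decision for the sponsor and the IDMC, and none is suggested here.

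The cost is one sentence in section 9.7, issued through a protocol amendment. No analysis, sample size or data collection changes. If the lead-in has been completed, a short note recording the DLT counts at each review and the threshold applied would serve the same purpose.

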5.1 DOSE MODIFICATIONS

Subjects will be monitored continuously for adverse events (AEs) while on study therapy. Subjects will be instructed to notify their physician immediately for any and all AEs. Adverse events will be graded according to CTCAE version 4.0. Dose modifications will be made for:

- a) Subjects who experience an adverse event of grade 3 or greater that is probably related to the study drug will be withdrawn from study and will be followed until the resolution of toxicity.
- b) Subjects who experience an adverse event of grade 3 or greater that is possibly related to the study drug will not be retreated with subsequent cycles until the adverse event resolves to grade 1 or less. Subjects who require greater than 14 days of treatment delay due to toxicity that is possibly related to the study drug will be removed from the study and followed until resolution of toxicity.

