The criteria for the early termination for efficacy (rejection of null hypothesis) or to accept the null hypothesis will be based on the group sequential design. If the test statistics crosses the pre-specified boundaries for type I error (0.0029, 0.010, and 0.012; cumulative alpha of 0.0029, 0.013, and 0.025 respectively) the trial will stop for efficacy. Otherwise, the trial continues to the next stage. The beta levels for stopping the trial for accepting the null hypothesis will be included in the detailed statistical analysis plan for the Independent Data Monitoring Committee (IDMC).

If efficacy is established at an interim analysis, enrollment will be stopped and the control group will be allowed to crossover. All subjects will be followed up until death, loss to follow-up, or termination of the study.

Randomization Strategy:

A central randomization scheme with Interactive Web Response System (IWRS) will be employed to facilitate effective randomization and allocation concealment. The scheme will involve a block randomization technique, randomly assigning participants within blocks based on a 2:1 allocation ratio. The randomization sequence will be generated using Oracle Clinical Remote Data Capture application (Oracle Corporation, Redwood City, CA, USA).

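### The lead-in suspension trigger in Protocol 9.7 gives a share (33%) and a count (6) that disagree at both planned looks; print one pooled count per look

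*Protocol*

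**What the plan says.** Under Protocol 9.7, "the Sponsor will conduct a blinded review of adverse event data for the first 10+10 patients enrolled on this protocol at that dose level". Data are reviewed once the first 10 patients have completed two cycles (28 days) and again after the second 10. On the 2:1 allocation, "approximately 6 of the first 10 and 13 of the first 20 patients will have received Xilonix".

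The commitment is: "The Sponsor will voluntarily suspend enrollment on the study, immediately and at any time upon review of safety data during the lead in period". The condition is that at least 33%, with at least 6 in brackets, "of patients have experienced a dose limiting toxicity (DLT). In this event, enrollment will be suspended pending further IDMC review". The text states no denominator and gives no separate count for the first look. A DLT is a clinically significant grade 3 or higher event or laboratory value in the first two cycles, at least possibly related to study drug and not attributed to progression, intercurrent illness or concomitant medication.

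Once the trigger is met, "the IDMC will be asked to review un-blinded data and make a recommendation regarding the safety of the dose level in this population".

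**The concern.** A suspension rule should give one answer for one set of data. Here two people applying 9.7 in good faith can reach opposite decisions, because the percentage and the bracketed count are different thresholds and neither is given precedence. The review is blinded, so the count is pooled over both arms. The natural denominators are therefore 10 and 20, and the two figures conflict at each. At stake is whether, and how early, enrollment stops for IDMC review if 7.5 mg/kg proves toxic in the first 20 patients.

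**Working it through.** **Inputs, all from Protocol 9.7:** share 33%; count 6; looks at n = 10 and n = 20, both arms pooled; about 6 and 13 of these patients on Xilonix.

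**Step 1. Try to reproduce the printed 6.** The smallest count meeting the share is 0.33 × n, rounded up.

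- n = 20: 0.33 × 20 = 6.6, so 7 (7/20 = 35%; 6/20 = 30%)
- n = 10: 0.33 × 10 = 3.3, so 4 (4/10 = 40%; 6/10 = 60%)
- n = 13, Xilonix only: 0.33 × 13 = 4.29, so 5 (6/13 = 46%)
- n = 6, Xilonix only: 0.33 × 6 = 1.98, so 2 (6/6 = 100%)

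Using one third instead of 0.33 gives the same counts. A threshold of 6 matches 33% only at n = 16, 17 or 18 (for example 0.33 × 18 = 5.94, so 6), and none of these is a planned look. Cutting 6.6 down to 6 would give the printed figure, but 6 of 20 is below 33%.

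**Step 2. Where the decisions differ.**

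| Data | Share of 33% | Count of 6 |
|---|---|---|
| 4 or 5 DLTs in 10 | suspend | continue |
| 6 DLTs in 20 | continue | suspend |

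**Step 3. How much the choice matters.** The documents give no DLT rates, so these are assumptions: Xilonix rate p = 0.33; placebo rate q = 0, 5, 10, 15, 20%. With X ~ Bin(Xilonix n, p) and Y ~ Bin(placebo n, q), the chance of reaching k is P(X + Y ≥ k). The split is 6+4 at the first look and 13+7 at the second.

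Example, first look, q = 0: P(X ≥ 4) = 15 × 0.33⁴ × 0.67² + 6 × 0.33⁵ × 0.67 + 0.33⁶ = 0.0799 + 0.0157 + 0.0013 = 0.097. P(X ≥ 6) = 0.33⁶ = 0.0013.

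| Rule, p = 0.33 | q=0 | 5% | 10% | 15% | 20% |
|---|---|---|---|---|---|
| First look, ≥4 of 10 | 0.10 | 0.14 | 0.19 | 0.24 | 0.29 |
| First look, ≥6 of 10 | 0.001 | 0.005 | 0.012 | 0.020 | 0.031 |
| Second look, ≥6 of 20 | 0.23 | 0.31 | 0.38 | 0.45 | 0.52 |
| Second look, ≥7 of 20 | 0.10 | 0.15 | 0.21 | 0.27 | 0.33 |
| Whole lead-in, 4th in 10 or 6th in 20 | 0.26 | 0.33 | 0.41 | 0.48 | 0.56 |
| Whole lead-in, count 6 alone | 0.23 | 0.31 | 0.38 | 0.45 | 0.52 |
| Whole lead-in, share checked at 10 and 20 only | 0.15 | 0.21 | 0.28 | 0.35 | 0.42 |
| Whole lead-in, share checked at every patient from 10 to 20 | 0.26 | 0.34 | 0.41 | 0.48 | 0.55 |

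The last row is by simulation with random order within each cohort; the others are exact. Block size is not given. If the first ten split 7+3, the first-look figures become 0.17 to 0.33 for ≥4 and 0.007 to 0.040 for ≥6.

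**Step 4. Price of the clearer rule.** Chance of suspension at lower true Xilonix rates, same q values, for 4th in 10 or 6th in 20 against count 6 alone:

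- p = 10%: 0.002/0.008/0.020/0.038/0.063 against 0.001/0.004/0.011/0.023/0.042
- p = 20%: 0.04/0.08/0.12/0.17/0.23 against 0.03/0.06/0.10/0.14/0.20

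The largest increase is about 2 points at 10% and 4 points at 20%.

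**The case against.** The mildest reading is that 6 is loose rounding meant for the full 20. That narrows the conflict there to one patient, but 6 of 20 is still 30%, and the first look is left without a count although the rule applies throughout the lead-in.

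It is fair to say that the practical gain is modest. If the share is checked continuously from patient 10, as the at-any-time wording allows, it performs almost exactly like the proposed counts. The 11 to 14 point advantage appears only if the share is checked at 10 and 20 alone. A true rate of 33% also sits badly with Protocol 8.2: in the completed controlled trial at 7.5 mg/kg (N=309), most of the common events were grade 1 or 2, with similar prevalence on placebo. Other protections exist. "Subjects who experience an adverse event of grade 3 or greater that is probably related to the study drug will be withdrawn from study" (Protocol 5.1); "A report of the adverse event data at each of these two time points will be submitted to the FDA within 10 days" (9.7); and SAP section 4 promises continuous early-toxicity monitoring until the first interim analysis. All of this bears on the stakes, not on the contradiction.

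Stating that whichever figure is met first governs would keep both printed numbers and give 4 and 6 at the two looks. It leaves the running denominator undefined between and before them: one DLT in the first three patients is already 33%.

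A reader might also infer that pooling leaves the IDMC blind to Xilonix toxicity and that by-arm DLT counts are needed at each look. The documents do not support that. Protocol 7.1 gives the IDMC unblinded safety data at specified time points, 10.1 has it formed before initiation to monitor safety, and the charter that SAP section 4 refers to is not among the documents. Nor would a by-arm threshold detect more: ≥5 of 13 on Xilonix is reached with probability 0.44 at a true 33%, the same as pooled ≥5 of 20 with no placebo DLTs, and less than the pooled rule once placebo DLTs occur.

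Finally, the lead-in may be over. SAP 7.1 dates the 7.5 mg/kg dose from version 3.0 and the SAP table shells are for version 3.6. The documents do not say.

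**Conclusion.** The trigger is wrong as written. The share and the count are different thresholds at both planned looks, no planned denominator reconciles them, and neither document says which governs. This rests on arithmetic alone.

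The consequence is small and depends on assumed rates. Settling on 4 of 10 and 6 of 20 mainly brings suspension forward to the first look. Over the whole lead-in it adds about 2 to 3 points against a count of 6. Against the share it adds between about zero and 11 to 14 points, depending on how often the share is checked. It would be too strong to say that the present wording exposes patients to a material undetected risk. This is a minor correction worth making.

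**What to change.** In Protocol 9.7, replace the paired figures with one pooled, blinded count per look, applied as soon as it is reached: suspend enrollment at the 4th DLT among the first 10 patients or the 6th among the first 20. These are the stricter of the two printed figures at each look. Drop the percentage, or print the matching 40% and 30%. DLT counts in a fixed cohort can only rise, so the rule works between looks without unblinding. The IDMC referral and the FDA reports stay as they are.

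Choosing 6 and not 7 at the second look is a judgement. A strict 33% would be 4 and 7, and either pair removes the ambiguity. If the lead-in is already complete, no amendment is needed; record which figure was applied at each look.

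The cost is one sentence, plus the small rise in false suspensions shown above.
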